**c. Local Number of Subjects**

This is a pilot study which aims to enroll 30 patients locally, 15 per arm.

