**e. Study Endpoints**

Primary Outcome: Complete wound closure of a chronic, non-healing wound at 6 weeks.

- a. Complete wound closure will be defined as skin reepithelialization without drainage or dressing requirements confirmed at two consecutive study visits 2 weeks apart. Incidence of complete wound closure in the control group will be compared to that of the treatment group.

Secondary Outcome: Rate of wound closure over 6-week study period.

- a. PUSH Tool 3.0 scores and clinical photos will be compared between the control group and treatment group to evaluate the rate of wound closure over the course of the 6-week study period.

Tertiary Outcome: Compliance and patient satisfaction with immunonutrition supplementation regimen.

- a. Patient satisfaction surveys and compliance logs will be evaluated to assess feasibility of implementing an immunonutrition regimen into standard wound care.

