#### **h. Statistical Analysis**

Summary statistics will be used to summarize measurements and assessed for unadjusted differences across treatment condition. Student's t-tests will be used for continuous measures, exact binomial tests for dichotomous measures, and chi-square tests for categorical measures.

The main outcome of interest is the proportion of wound closed at the end of 6 weeks which we will model in a generalized linear models framework

$$E[g(y_i)] = \beta_0 + Trt_i\beta_1 + Z_i\gamma$$

where  $y_i$  is the outcome measure of interest of the  $i$ th participant,  $Trt_i$  is an indicator variable of whether the participant was assigned to the treatment condition,  $Z_i$  is a vector of covariates for which we will adjust the model (i.e., initial wound size, diabetes etiology, sex, race, and age), and  $\gamma$  is a vector of regression parameters. We have written the outcome in terms of a link function ( $y_i$ ) to emphasize that we will estimate a linear regression model (identity function) as well as a zero-one augmented beta regression model for which we will choose from among several link functions (logit, log, log-log, and complementary log-log). Anticipating that we will have outcomes of exactly 0% or 100% reduction of the wound size, we will model the transformed outcome

$$y_i^* = \frac{99y + 0.5}{100}$$

Our focus is on the null hypothesis  $H_0: \beta_1 = 0$ . We will evaluate this null hypothesis using a Wald test of the parameter based on an appropriate variance estimate – chosen from model-based, sandwich, or sandwich based on an evaluation of the implied dispersion properties of the model-based variance estimator.

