Other secondary outcome variables to be modeled include the time to complete healing (Cox proportional hazards regression), rate of closure (Cox proportional hazards regression), presence of infection (binary regression), and need for surgery (binary regression). Cox proportional hazards models will be used to interpret the relative hazards between treatment conditions. The proportional hazards assumption will be checked using Schoenfeld residuals and accelerated failure time (parametric) regression models will also be evaluated. Binary outcomes will be modeled using various link functions (logit and log). Exponentiated coefficients for logit-link models will be interpreted as odds ratios, and exponentiated coefficients from log-link models will be interpreted as risk ratios. Binary outcomes may be relatively rare, and so we will also

estimated binary models using exact statistics. In addition, we will investigate bias through estimation of bias-corrected models.

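### No covariate-adjusted analysis is specified for complete closure, the named primary outcome, although baseline wound size is recorded and used in the model for proportion of wound closed

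*Combined protocol and SAP*

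**What the plan says.** All references are to the combined protocol and SAP.

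- **Section 6e, Study Endpoints:** "Primary Outcome: Complete wound closure of a chronic, non-healing wound at 6 weeks". The comparison is described in one sentence: "Incidence of complete wound closure in the control group will be compared to that of the treatment group". No test, model or covariate is named there.
- **Section 6c:** "This is a pilot study which aims to enroll 30 patients locally, 15 per arm". No power, effect size or closure rate is given.
- **Section 6h, first paragraph:** "Summary statistics will be used to summarize measurements and assessed for unadjusted differences across treatment condition", followed by "Student's t-tests will be used for continuous measures, exact binomial tests for dichotomous measures, and chi-square tests for categorical measures".
- **Section 6h, model paragraph:** the main outcome is the proportion of wound closed at 6 weeks. Its model adjusts for "initial wound size, diabetes etiology, sex, race, and age", and the null hypothesis on the treatment coefficient belongs to this model.
- **Section 6h, other secondary outcomes:** Cox models for time to complete healing and rate of closure, and binary regression for infection and need for surgery. A further sentence says that binary outcomes will be modelled with logit and log links, with exact and bias-corrected versions. No covariates are listed, and complete closure as a yes/no outcome is not mentioned.
- **Section 6f:** wound size is recorded with the PUSH Tool before randomization. Allocation follows a pre-defined table, with no stratification described.

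**The concern.** Small ulcers can be expected to close within 6 weeks more readily than large ones, and the plan puts initial wound size first in its own covariate list. Yet the documents assign no analysis using wound size to the endpoint that 6e calls primary. Two things are at stake. With 15 patients per arm, the arms can differ in ulcer size by chance, and an unadjusted difference in closure then mixes that imbalance with the treatment effect. If size is strongly prognostic, ignoring it also leaves explainable variation in the error. For a pilot, whose main product is an estimate for a later trial, the first matters more.

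**Working it through.** **1. Which analysis reaches which outcome (6e and 6h)**

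| Outcome | Status in the documents | Analysis stated | Covariates stated |
|---|---|---|---|
| Complete closure, yes/no | Primary (6e) | Only "exact binomial tests for dichotomous measures" clearly applies | None |
| Proportion of wound closed | Main outcome (6h) | Linear and beta regression | Five, including initial size |
| Time to complete healing, rate of closure | Secondary (6h) | Cox | Not stated |
| Infection, surgery | Secondary (6h) | Binary regression | Not stated |

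The documents contain one covariate list, and it is attached to the second row.

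**2. Chance imbalance in baseline size**

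Input: 15 per arm (6c), simple allocation assumed.

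- SD of the difference in mean baseline size = sqrt(1/15 + 1/15) = sqrt(2/15) = 0.37 baseline SDs.
- P(|difference| > 0.25 SD) = 49%.
- P(|difference| > 0.5 SD) = 17%, so about 17%/2 = 8.5% in each direction.

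**3. What an imbalance does to the estimate**

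Assumptions: no treatment effect, 30% closure in both arms, odds ratio for closure of 2 or 4 per SD of size; 100,000 simulated trials each. When treated wounds happen to be smaller by more than 0.5 SD, the treated arm's closure rate looks higher by about 9 points (odds ratio 2) or 15 points (odds ratio 4).

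**4. Power gained by adjusting for size**

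The plan gives no power figure to reproduce. Closure rates, the correlation and a two-sided 5% level are assumptions. Closure is a dichotomized latent normal variable with correlation r to log baseline size, so latent residual variance is 1 - r²: 0.91, 0.75 and 0.51 at r = 0.3, 0.5 and 0.7. Power is for Firth (penalized-likelihood) logistic regression, without and then with baseline size, from runs of 800 to 1,500 trials per setting.

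| Closure, control vs treatment | r = 0.5 | Gain at r = 0.5 | Gain at r = 0.3 |
|---|---|---|---|
| 10% vs 30% | 25% to 26% | 1 | 0 |
| 20% vs 40% | 17% to 21% | 4 | 3 |
| 10% vs 40% | 43% to 49% | 6 | 2 |
| 30% vs 60% | 32% to 39% | 7 | 2 |
| 30% vs 70% | 58% to 65% | 7 | 1-3 |
| 20% vs 60% | 57% to 67% | 10 | 1-3 |
| 20% vs 70% | 82% to 89% | 7 | 1-3 |

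Other runs at r = 0.5 for 20% vs 60% gave 59% to 66%, 60% to 68% and 62% to 68%, so the 10 is the top of a 6-10 range. At r = 0.7 the gain was 11-17 points for the last three rows and 14 for 30% vs 60%. These figures should not be carried over to 20-point effects. The Monte Carlo standard error of one power figure is at most sqrt(0.25/800) = 1.8 points. Type I error of the adjusted analysis was about 4-5%.

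**5. A second model as a check**

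Logistic closure, 30% vs 60%, 3,000 trials, power at critical values set to give 5% under the null:

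| Odds ratio per SD of size | Unadjusted | Adjusted for size |
|---|---|---|
| 1 | 39% | 39% |
| 2 | 37% | 41% |
| 4 | 37% | 49% |

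One covariate costs essentially nothing when size is irrelevant and gains about 12 points when it is strongly prognostic. The critical values had to be reset because penalizing each model by its own information matrix let the unadjusted test reject about 8% of null trials. The form of the penalized test therefore needs stating.

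Using all five covariates lowered nominal power from 41%, 44% and 47% (size alone) to 35%, 36% and 39%, a loss of 6-8 points, with the other four simulated as unrelated to closure.

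**The case against.** The strongest reply is that 6h does not confine closure to an unadjusted test. It says without restriction that binary outcomes will be modelled, with exact and bias-corrected versions, and closure is binary. This stands in part. A reader might infer that the plan rules out adjustment of closure; the text does not support that. But the sentence sits among the secondary outcomes and names neither closure nor covariates, so the analysis remains unspecified.

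Second, 6h attaches its hypothesis test to proportion closed, already adjusted for wound size. If that outcome governs, the main analysis has its adjustment. This also stands: 6e and 6h conflict, and settling that comes first. If 6e governs, the gap remains.

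Third, a reader might infer inflated type I error. The documents do not support that, because randomization protects the unconditional rate. In the null trials of step 3 with an imbalance above 0.5 SD in either direction, a two-arm exact test rejected in 2.8% (odds ratio 2) or 4.2% (odds ratio 4). That is above its own averages of 1.8% and 1.6% but below 5%. What remains is distortion of the estimate.

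Fourth, a definite loss of power cannot be claimed. The plan gives no prognostic strength for size, and large treatment effects are not documented. Closure must be confirmed at two visits 2 weeks apart. If both must fall within 6 weeks, the wound must be closed by week 4, so low rates are plausible, and there the gain is small.

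Finally, the PUSH form scores size in bands, so area might not be kept. This fails: the proportion-closed model itself needs measured area.

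**Conclusion.** The point holds as a gap in specification: the documents name complete closure as primary and specify no covariate-adjusted analysis for it. The firm consequence is exposure of the closure estimate to imbalance in ulcer size. The probability of an imbalance above 0.5 SD is about 17%. The resulting distortion when treated wounds are the smaller ones is about 9-15 points, if size carries an odds ratio of 2-4 per SD and closure is 30%.

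The power gain is conditional: about 0-3 points at correlation 0.3, about 1-10 at 0.5 (smallest for 20-point effects), and about 11-17 at 0.7 for effects of 30 points or more. All these closure rates, correlations and odds ratios are assumptions. Power differences between an exact test and Firth regression reflect the choice of test and are not part of this point. The change is worth making because it is cheap; the gap does not invalidate a 30-patient pilot.

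**What to change.** 1. Reconcile 6e and 6h so that one outcome is primary.
2. For complete closure, state in 6h: *Complete closure at 6 weeks will be compared between arms by Firth (bias-corrected) logistic regression with treatment and log baseline area of the index wound as the only covariate. The test and confidence interval for treatment will use the profile penalized likelihood, with the full-model penalty retained under the null.*
3. Keep incidence by arm and the unadjusted exact two-arm comparison as supportive results. Do not carry all five covariates into the closure model.
4. Define the index wound, since eligibility allows more than one, and record its baseline area in cm² as well as the PUSH sub-score.
5. State which covariates enter the binary and Cox models for the secondary outcomes.

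The cost is SAP wording, an index-wound definition and one extra model on a measurement already taken at Visit 0. The downside is that the odds ratio is conditional on wound size and will not match the crude closure rates, which needs a sentence of explanation in the report.

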  - a. If randomized to the control group (SOC only), patients will receive standard of care defined as sharps debridement, appropriate dressing, and offloading. If randomized to the treatment group (SOC + Immunonutrition), subjects will receive standard of care defined as sharps debridement, appropriate dressing, and offloading in addition to a 6-week supply of Omega-3 fatty acids (soft gel form, 2 pills per day, total of 1.68 grams) and L-Arginine/Vitamin C (powder form, to be mixed with 8 oz liquid, 1 scoop once daily, total of 4.5 grams L-arginine and 500 mg vitamin C). Subjects will also be provided a compliance log with detailed instructions for taking and tracking supplements.
5. Patients will be scheduled for biweekly wound checks with their provider (weeks 2, 4, 6). Wound characteristics will be documented at each follow up visit using the PUSH Tool 3.0, images of the wound will be obtained, and an interval history and physical exam will be documented. The provider will verify and document concomitant medications in the patient's chart. The provider will visualize and evaluate any additional wounds that are present (new or present at time of enrollment) and record characteristics in the patient's chart. Patients will complete a questionnaire detailing their pain level (VAS), symptoms experienced during the treatment phase, and any unscheduled visits to emergency departments/urgent care centers. This will be completed via a paper survey in clinic during their office visit (Appendix 4). On weeks where an office visit is not scheduled (weeks 1, 3, 5), a research coordinator will call the patient and collect survey responses (Appendix 3).
6. At the final office visit (week 6), plantar pressure profiles will be recorded via the Tekscan Pressure Mat, and clinical plantar weight-bearing images will be captured. Patients randomized to receive the oral immunonutrition supplementation will complete an additional survey detailing their satisfaction with the treatment plan and any additional thoughts they would like to share (Appendix 5) and return the completed compliance log

(Appendix 6). Patients in the treatment arm will have CMP and lipid panel labs drawn at this timepoint or within 3 months of study completion.

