7. A follow-up safety visit will be conducted by the provider for patients randomized to the treatment group 6-8 weeks after the week 6 office visit. This visit is more than 5 half-lives after supplementation discontinuation and will allow for capture of adverse events that may occur after completion of dosing. The wound will be visualized during this visit. Adverse events and wound details will be documented in the patient's chart. This visit will be conducted in-office if the patient is already scheduled to see their provider within the visit window. If the patient is not scheduled to see their provider, this visit may be conducted virtually through EPIC.
8. Patient charts will be monitored throughout the patient's participation in the study for any signs of infection, unscheduled visits, calls to the provider, and/or onset of severe adverse events. Patient charts will continue to be monitored for one year following the completion of the study to assess ulcer recurrence rates.

The schedule of events is outlined below and is pictured in Appendix 1:

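### Section 6(e) makes complete closure the primary outcome, but section 6(h) tests its only stated hypothesis on a different variable, the proportion of wound closed, and nothing ranks the two

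*Combined protocol and SAP*

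**What the plan says.** Section 6(e), on study endpoints, ranks outcomes as primary, secondary and tertiary. The first entry is "Primary Outcome: Complete wound closure of a chronic, non-healing wound at 6 weeks". It is a yes/no event for each patient: the skin has re-epithelialised, with no drainage and no need for a dressing, "confirmed at two consecutive study visits 2 weeks apart". The comparison is also given: "Incidence of complete wound closure in the control group will be compared to that of the treatment group". The next entry is "Secondary Outcome: Rate of wound closure over 6-week study period", based on PUSH scores and photographs. The tertiary entry is compliance and satisfaction.

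Section 6(h), on statistical analysis, begins with general unadjusted tests, including exact binomial tests for dichotomous measures. It then says: "The main outcome of interest is the proportion of wound closed at the end of 6 weeks". This variable is modelled by linear regression and by zero-one augmented beta regression, adjusted for initial wound size, diabetes etiology, sex, race and age. The null hypothesis that β1 = 0, tested by a Wald test, belongs to this model. No other null hypothesis is written in the plan.

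The following paragraph of 6(h) lists further outcomes and calls them secondary: time to complete healing and rate of closure (both by Cox regression), infection, and need for surgery (both by binary regression).

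**The concern.** A trial that ranks its endpoints and also plans a hypothesis test must say which endpoint the test decides. Here the word primary is attached to one variable, while the words main outcome and the hypothesis are attached to another. The proportion of wound closed is not listed in 6(e), and 6(h) assigns no analysis by name to the incidence of closure at week 6.

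If the two analyses disagree, the authors could present either as the planned headline result and cite the protocol for it. A reader could not tell whether that choice was made before or after the results were known.

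**Working it through.** **1. Are the two variables the same?** A loose reading would take the 6(h) variable to be the proportion of patients healed. The text rules this out. The outcome carries a participant index, it is fitted with beta regression, and the stated reason for transforming it is "Anticipating that we will have outcomes of exactly 0% or 100% reduction of the wound size". The transform is y* = (99y + 0.5)/100, so y = 0 becomes 0.005 and y = 1 becomes 0.995. That is a fraction between 0 and 1 for each patient.

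The variables can also differ within one patient. A wound first seen closed at week 6 shows 100% reduction under 6(h) but has no second confirming visit under 6(e). Wound checks are at weeks 2, 4 and 6, and the later safety visit is only "for patients randomized to the treatment group 6-8 weeks after the week 6 office visit".

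**2. Does anything rank them?** The nearest 6(e) entry is the secondary rate of closure, but 6(h) models rate of closure separately by Cox regression. The closure event itself appears by name in 6(h) only as time to complete healing, labelled secondary. Its week-6 incidence is reached only through the general lines on dichotomous measures and binary models. Exact binomial does not identify a two-sample test.

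**3. How often would the choice matter?** The plan has no figure to reproduce: 30 patients (15 per arm) is given without alpha, power, effect size or closure rates. Everything below except n = 15 per arm is therefore assumed, including the two-sided 5% level.

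*Exact power for closure.* Sum the product of Binomial(15, p0) and Binomial(15, p1) probabilities over the rejection region.

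| Closure, control vs treatment | Fisher | Boschloo (maximum size 0.043) |
|---|---|---|
| 20% vs 50% | 0.246 | 0.373 |
| 20% vs 60% | 0.447 | 0.599 |

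For scale: with 3 of 15 controls closed, Fisher's test needs at least 10 of 15 in the treatment arm. An observed 3/15 vs 9/15 (20% vs 60%) is not significant.

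*Joint behaviour.* Simulation of 40,000 trials. Closed wounds have y = 1; unclosed wounds follow a Beta distribution with precision 4 and the mean reduction shown. The transform is applied, then a two-sample t-test on y* is set against Fisher's test on closure.

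| Scenario (closure; mean reduction if unclosed) | Linear | Fisher | Disagree | Either significant |
|---|---|---|---|---|
| No effect (20/20%; 50/50%) | 0.052 | 0.016 | 0.053 | 0.060 |
| Only closure differs (20/60%; 50/50%) | 0.460 | 0.446 | 0.203 | 0.554 |
| Both favour treatment (20/60%; 40/60%) | 0.837 | 0.449 | 0.395 | 0.840 |

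The disagreement splits as follows.
- Only closure differs: linear alone 0.554 − 0.446 = 0.108; Fisher alone 0.554 − 0.460 = 0.094.
- Both favour treatment: linear alone 0.840 − 0.449 = 0.391; Fisher alone 0.840 − 0.837 = 0.003.

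*Sensitivity of the disagreement rate.*
- Beta precision from 2 to 8: 0.241 to 0.173 when only closure differs; 0.349 to 0.439 when both favour treatment.
- Boschloo in place of Fisher: 0.230 and 0.262.
- Linear test adjusted for five assumed covariates (20,000 trials): 0.236 and 0.349 if the covariates are not prognostic; 0.245 and 0.371 if wound size is prognostic.
- Smaller closure effect, 20% vs 40%: about 0.12 with equal shrinkage; about 0.25 with shrinkage of 40% vs 50%.

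*Type I error.* Two independent tests at 5% would give 1 − 0.95² = 0.0975. The simulated figure is 0.060, because the variables are correlated and Fisher's test is conservative.

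**The case against.** The strongest reply is that 6(e) is the only place that formally ranks outcomes, and 6(h) never uses the word primary. Because 6(h) goes on to introduce its next outcomes as other secondaries, the proportion-closed model can be read as a secondary analysis, leaving closure as the primary with a label to correct. Closure is also not wholly without analysis, since the general lines on dichotomous measures and binary models would cover it. This reading is possible, but calling the variable the main outcome and focusing the hypothesis on it point the other way, and nothing in the plan settles the matter.

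The figures can also be challenged. The 39% partly reflects the conservatism of Fisher's test; against Boschloo it is 26%, although the figure for the closure-only case rises from 20% to 23%. A 40-point closure effect is a large assumption, and smaller effects give about 12% to 25%. The planned beta regression was not simulated, a t-test stands in for the Wald test, and the two-visit confirmation was not modelled. These points stand. They change the size of the illustration but not the contradiction in the text.

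Finally, this is a 30-patient pilot with no stated power. That lowers the stakes of any single p-value, but it does not excuse two competing headline results in a plan that ranks its outcomes and tests a hypothesis.

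**Conclusion.** The concern holds. Sections 6(e) and 6(h) name different variables as the one that matters, the only written hypothesis is on the variable missing from the 6(e) list, and no text ranks them. This conclusion rests on the wording alone.

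Its practical size depends on assumed rates. Across the non-null scenarios above, in all of which closure favours treatment, the two tests disagree on significance in about 12% to 44% of trials of this size. Type I error is little affected (6.0% for either test when neither variable has an effect). The damage is that the trial's result is undefined and could be chosen after the data are seen.

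**What to change.** Before outcome data are seen, make 6(e) and 6(h) name the same primary variable.

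- **Default:** state in 6(h) that the primary analysis variable is complete closure as defined in 6(e). Replace the general exact binomial wording, for this outcome, with one named two-sample exact test (Boschloo or Fisher, for example) at a stated alpha. Report the risk difference with a confidence interval. Label the proportion-closed model and its β1 test secondary, and keep a covariate-adjusted analysis of closure as supporting.
- **Alternative:** amend 6(e) so that the proportion of wound closed is primary and complete closure is secondary.
- **Under either choice:** add a sentence to 6(e) on how a wound first seen closed at week 6 is counted, since only the treatment arm has a scheduled study visit after that.

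The change is wording only: no added patients, visits or measurements. The default has two costs. First, it may lose power. On the assumed 20% vs 60% closure, Fisher has 45% and Boschloo 60%, against 84% for the linear test when shrinkage also favours treatment. At 20% vs 50% the exact tests have 25% and 37%. Second, the headline comparison would no longer carry the planned adjustment for the five covariates, which would move to the supporting analysis.

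### Section 6h names a zero-one augmented beta model but in effect fits an ordinary one, and its test of β1 has no fixed lead model, link or variance, although several permitted versions miss a 5% level at n = 30

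*Combined protocol and SAP*

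**What the plan says.** Section 6h (Statistical Analysis) states: "The main outcome of interest is the proportion of wound closed at the end of 6 weeks". The model adjusts for "covariates for which we will adjust the model (i.e., initial wound size, diabetes etiology, sex, race, and age". On the form of the model it says "we will estimate a linear regression model (identity function) as well as a zero-one augmented beta regression model for which we will choose" from "several link functions (logit, log, log-log, and complementary log-log". On boundary values: "Anticipating that we will have outcomes of exactly 0% or 100% reduction of the wound size, we will model the transformed outcome", where y* = (99y + 0.5)/100. There is one null hypothesis, β1 = 0, tested by a Wald test with a variance estimate "chosen from model-based, sandwich, or sandwich based on an evaluation of the implied dispersion properties of the model-based variance estimator".

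Section 6c gives the size: "This is a pilot study which aims to enroll 30 patients locally, 15 per arm".

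The text gives no significance level, no rule for choosing the link, no cut-off for the dispersion check, no form of sandwich estimator and no reference distribution for the Wald statistic. It does not say which of the two models leads.

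Section 6e defines the primary outcome differently: complete closure, yes or no, confirmed at two visits two weeks apart.

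**The concern.** Two things do not fit together.

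First, zero-one augmentation and the transform are alternative ways of handling exact 0s and 1s. Used together, the transform leaves the augmentation nothing to model. The distinction matters for the test. An augmented model on untransformed y has a zero part, a one part and an interior part, and treatment could enter each of them, so a single β1 would not describe the treatment effect unless a contrast were stated. An ordinary beta model on y* does have one β1.

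Second, the test is not fixed. The linear β1 is a difference in mean proportion closed; the beta β1 is a difference on the logit, log, log-log or complementary log-log scale. The open choices therefore change what is estimated as well as the p-value. If some permitted versions reject a true null too often in a trial of this size, a reader of the result cannot tell whether its p-value can be taken at face value, or whether the version was settled before the result was seen.

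A lesser point is that section 6h describes the outcome both as proportion closed and as reduction in size, and gives no rule for a wound that grew.

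**Working it through.** **Inputs.** From the plan: 30 patients, 15 per arm (6c); five covariates, two models, four links, a Wald test, and the transform (6h). Assumed, because the plan gives none: a two-sided 5% level, the outcome mixes and the covariate distributions. The plan has no power or error-rate figure to reproduce.

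**1. The transform.**
- y = 0: (0 + 0.5)/100 = 0.005.
- y = 1: (99 + 0.5)/100 = 0.995.
- Every y from 0 to 1 therefore lands strictly inside (0, 1). The zero and one parts have no observations, and the likelihood is that of an ordinary beta regression. It can be fitted.
- y* reaches 0 at y = −0.5/99 = −0.00505. If reduction is read as signed, a wound that grew by 20% gives (−19.8 + 0.5)/100 = −0.193, which a beta model cannot take. Scored as 0% closed, it causes no difficulty.

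**2. The number of permitted tests.** One linear model plus four beta links is five models. With model-based or sandwich variance, 5 × 2 = 10 Wald tests of β1, before counting sandwich forms and reference distributions. The sandwich option appears twice in the list; a word may have been lost in reading the PDF, so I give that no weight.

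**3. Size of the linear test, without simulation.** Intercept, treatment and five covariates with one term each make 7 mean parameters, leaving 30 − 7 = 23 degrees of freedom. With normal errors, a model-based test referred to the normal instead of the t distribution rejects a true null with probability 2P(t23 > 1.96) = 6.2%. If race or etiology needs extra terms and 20 df remain, it is 6.4%.

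**4. Illustrative null simulations.** 15 per arm, five covariates, no treatment effect, each test fixed in advance. Set I: about 1,000 trials per mix; 5% zeros and 30% ones, 10% and 20%, or 0% and 15%; the rest Beta(2,2), Beta(2,2) and Beta(3,2); outcome unrelated to covariates. Set II: 3,000 trials per scenario; closed 26, 40, 0 and 11%; scored 0 (unchanged or grown) 9, 3, 0 and 18%; wound size related to healing. HC0 is the uncorrected sandwich; HC1 and HC3 are small-sample corrections.

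| Test (rejection of a true null, %) | Set I | Set II |
|---|---|---|
| Linear, model-based, t | 4.1 / 5.2 / 4.1 | 4.7 / 4.7 / 5.2 / 5.8 |
| Linear, model-based, normal | 4.9 / 6.5 / 5.0 | 5.6 / 6.2 / 6.6 / 7.2 |
| Linear, HC0, normal | 9.4 / 12.0 / 9.2 | 9.9 / 11.0 / 10.9 / 11.2 |
| Linear, HC3, normal | not run | 3.7 / 3.6 / 3.8 / 4.7 |
| Beta-logit, model-based, normal | 7.2 / 9.1 / 11.6 | 8.4 / 6.7 / 9.6 / 10.6 |
| Beta-logit, sandwich, normal | 9.2 / 11.1 / 12.8 | 10.7 / 11.1 / 10.6 / 12.2 |

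Over all four links in Set II, the beta tests ran from 3.0 to 12.6% (model-based) and 6.1 to 14.2% (sandwich). In a further linear-model check (four assumed mixes, 4,000 trials each), HC1 with a t reference gave 5.2-6.2%. Monte Carlo error at a 5% rate is about 0.7 points in Set I and 0.4 in Set II.

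**5. What choosing adds.** In Set I, picking the beta link by best likelihood gave 8.4 / 10.3 / 13.7% with model-based variance, against 7.2 / 9.1 / 11.6% for a fixed logit link: 1.2, 1.2 and 2.1 points more. The fixed logit test already exceeds 5% by 2.2, 4.1 and 6.6 points. Most of the excess is thus small-sample Wald error, and selection adds to it. In Set II, the ten versions disagreed on p < 0.05 in 11.1-16.2% of null trials.

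**The case against.** The strongest reply is that this is a 30-patient pilot with no stated level or power, that looking at more than one model for a bounded outcome is sensible, and that the beta model is merely mislabelled. Part of this stands. The label error alone does not stop the analysis, and the pilot setting limits what hangs on the p-value. But section 6h sets a formal hypothesis test on what it calls its main outcome, and such a test needs one reproducible result. The second model can stay as a sensitivity analysis.

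Four stronger readings are tempting, and the documents do not support them.

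- A reader might infer that the plan doubles the false-positive rate. That figure belongs to HC0 with a normal reference. The plan allows it but does not specify it. HC3 with a normal reference, or HC1 with a t reference, gives about 4-6%.
- A reader might infer an error rate of 16-21%, from taking the smallest p of the ten versions (15.8-21.0% in Set II, 14.2-19.4% in Set I). No such rule is in the plan, which ties the variance to a dispersion check; the figure is only an upper bound.
- A reader might infer that the beta model fails for wounds that grew. It does so only under a signed reading. Proportion closed, with exact 0% outcomes expected, reads more naturally as floored at 0.
- A reader might take a lead test here to be the trial's primary analysis. Section 6e gives binary complete closure that role.

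**Conclusion.** The point holds, and the SAP should be changed. Two parts rest on algebra and text alone: the transform removes every exact 0 and 1, so the named model is not the one fitted; and nothing in the supplied text settles the model, the link or the variance for the test of β1.

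The size rests on assumptions: a two-sided 5% level, one term per covariate, and invented outcome mixes. Under them, the beta-logit model-based Wald test rejects a true null about 7-12% of the time and the linear HC0 test with a normal reference about 10-11%. The covariate-adjusted linear model with model-based variance and a t reference stays near 5%. These rates show direction and rough size; they are not properties of the trial's own data. Confidence is high on the ambiguity and moderate on the rates.

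**What to change.** Before any outcome data are seen:

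- **Beta model.** Make it consistent in one of two ways; the documents do not show which was meant. Either fit ordinary beta regression to y* with one named link and remove the term zero-one augmented, or keep y untransformed, fit the zero and one parts, and state the contrast tested. The second route has little to work with: at an assumed 5% zeros and 30% ones, 30 patients give 1.5 zeros and 9 ones on average.
- **Lead test for proportion closed.** Name one that is valid in small samples. Examples are the planned covariate-adjusted linear model with model-based variance and a t reference, or a re-randomisation test that follows the actual allocation scheme. Report the other model as sensitivity.
- **Variance.** Remove the data-driven choice. If a sandwich is kept anywhere, state its form, its correction and the reference distribution.
- **Wounds that grew.** Give one outcome definition and one scoring rule for both models, for example 0% closed, and do not drop these patients.
- **Status.** Reconcile sections 6e and 6h, and say what role this analysis has beside the binary primary outcome. Naming a lead test here does not make proportion closed primary.

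The cost is SAP wording. The downside is that a linear model is a cruder description of a bounded outcome, and the fixed p-value may be less favourable than another version's.
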